12.1 Rapid diagnostic tests

Pf-specific RDTs (First Response) will be performed on participants every time a blood sample is collected. RDTs will be performed according to the directions provided, using the blood transfer device and reagents provided by the manufacturer. Tests will be performed by study personnel, and results will be available within 15 minutes. The results of the RDT will be provided to the participant or their parent/guardian verbally, and will be recorded. Symptomatic and asymptomatic participants who test positive for malaria will be brought to their local health care facility for appropriate work-up and treatment with AL.

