1.6 Drug regimens

For an individual receiving TPE, the goal is to treat any existing reservoir of infection. Prevention of future infection, as possible given the half-life of the drug is an added bonus. In Swaziland, Artemether-lumefantrine (AL or Coartem) is the first line therapy for *Pf* infection. The drug is generally well tolerated with minimal adverse effects. Doses are weight adjusted for children and a pediatric dissolvable version is available. One challenge is that the drug requires frequent administration. The second dose is administered 8 hours after the first dose and then 1 dose is given twice daily for 2 more days. Also, due to lack of data, it is not indicated for children <5kg. Pregnancy during the first trimester is also a contraindication. Animal studies suggest that fetal absorption could lead to early pregnancy loss.

Dihydroartemisinin-piperazine (DP) is another safe and efficacious ACT regimen recommended by the WHO, and now recommended as a second line therapy for uncomplicated malaria in many countries. A recent Cochrane review of DP included 27 trials conducted between 2002 and 2010, enrolling 16,382 adults and children[9]. Most trials excluded infants aged less than six months or <5 kg as well as women who were pregnant or breastfeeding. In Africa, over 28 days, DP was superior to AL in that there was less treatment failure (PCR-unadjusted treatment failure: RR 0.34, 95% CI 0.30 to 0.39, nine trials, 6200 participants, high quality evidence). Although PCR-adjusted treatment failure was below 5% for both ACTs, it was consistently lower with DP (PCR-adjusted treatment failure: RR 0.42, 95% CI 0.29 to 0.62, nine trials, 5417 participants, high quality evidence). DP has a longer prophylactic effect on new infections that may last for up to 63 days (PCR-unadjusted treatment failure: RR 0.71, 95% CI 0.65 to 0.78, two trials, 3200 participants, high quality evidence). In a previous review of DP, an association was noted between DP and prolongation of the QT interval in two small observational trials. Prolonged QT interval is a cardiac conduction defect that can sometimes lead to fatal arrhythmias[10]. However, in the same Cochrane review, compared to AL, no difference was seen in prolonged QTc, and no cardiac arrhythmias were reported. The frequency of other adverse events is probably similar with both combinations.

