If an individual cannot safely be given DP, that individual will not be given medication for presumptive treatment. Pregnant women and breastfeeding women will be excluded. All girls ≥ 10 years of age will also be asked about menses. Those who have had menarche but have not menstruated in the past 4 weeks will also be excluded. Infants < 9 months of age or < 7 kg will also be excluded. For infants and children unable to take tablets, drugs will be crushed, mixed with water and administered as a suspension. No more than two courses of DP may be given within a 12-month period. Additionally, a second course of DP should not be given within 2 months after the first course due to the long elimination half-life of piperazine. Other contraindications include: severe malaria, young children who vomit (electrolyte disturbances can increase QTc), heart problems or rhythm disturbances, kidney or hepatic insufficiency, recent treatment with certain medications (antiarrhythmics, neuroleptics, antibiotics, non-sedating antihistamines, antimalarial agents, and others (cisapride, droperidol, domperidone, bepridil, dephemanil, probucol, levomethadyl, methadone, vinca alkaloids, and arsenic trioxide).

Individuals who cannot safely be given DP will be tested by RDT using the *Pf*-specific First Response RDT during the intervention visit. At the time that blood is collected for RDT testing, the same finger prick will be used to generate a slide and dried blood spot. Four spots of blood will be collected for each DBS. A second finger prick will be used to collect microtainer blood samples from RDT-positive individuals. Subjects testing positive by RDT will be referred to the closest health facility for treatment with a drug that is safe for them according to national policy.

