Appendix Z. TPE Safety Monitoring Committee

Terms of Reference (TOR)

Targeted Parasite Elimination (TPE) Pharmacovigilance and Adverse Drug Reactions Committee (Data and Safety Monitoring Committee) *for approval at December 2014, Committee Meeting*

This TOR provides the framework for the responsibilities and activities of the Targeted Parasite Elimination Pharmacovigilance and Adverse Drug Reactions Committee (Data and Safety Monitoring Committee). The committee shall oversee the safety of the study drug – dihydroartemisinin-piperazine (DP) or artemether-lumefantrine (AL) as an alternative to DP, and shall perform this function by receiving and reviewing all data on DP or AL administered to study participants and by providing appropriate advice to the Ministry of Health which includes the National Malaria Control Program (NMCP) and the Swaziland Ethics Committee (SEC).

1. Background and scope of the Committee

Swaziland is currently aiming for malaria elimination by 2015. A major part of the approach has been reactive case detection (RACD), or the testing of individuals around index cases as a way to identify and treat secondary infections. Although the approach is useful for finding infected individuals and hotspots, there are some technical and logistical challenges relating to the test and treat approach. Presumptive treatment without testing, also known as targeted parasite elimination (TPE), has potential to be more effective and feasible. The goal of TPE is to critically evaluate this approach versus RACD as a surveillance and response strategy for malaria elimination in Swaziland. The TPE Pharmacovigilance and Adverse Drug Reactions Committee was established in December 2014 to monitor the safe use of DP or AL in the study. Members of the committee are representatives of institutions overseeing pharmacovigilance and adverse drug reactions in Swaziland. The committee includes individuals from the Swaziland Malaria Elimination Advisory Group (General Committee), the Ministry of Health (pharmacovigilance), the World Health Organization (WHO) and non-governmental organizations such as Management Sciences for Health (MSH).

2. Roles and Responsibilities

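### Section 12.1 directs every RDT-positive participant to AL without exception, which conflicts with 1.6, 7.2 and 7.3; Appendix Z and the protocol also disagree on whether AL is a study drug alongside DP

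*Combined protocol and SAP*

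**What the plan says.** **Treatment of RDT-positives**

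- Section 12.1: RDTs "will be performed on participants every time a blood sample is collected", and those who test positive "will be brought to their local health care facility for appropriate work-up and treatment with AL". No arm, visit or patient group is set apart.
- Section 4.1: RACD residents with a positive RDT are sent to a local clinic for AL. No other drug is mentioned.
- Section 7.2: RACD positives are treated under national policy, given as AL first line and oral quinine second line for uncomplicated malaria.
- Section 7.3: TPE residents who cannot safely take DP are tested and, if positive, are "referred to the closest health facility for treatment with a drug that is safe for them according to national policy". AL is not named.
- Section 1.6, on AL: "Pregnancy during the first trimester is also a contraindication". It also says that AL is not indicated below 5 kg, for lack of data. Section 17.3 agrees on early pregnancy: it says that ACTs in general are not recommended in the first trimester.

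**Presumptive treatment and the study drug**

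- Section 7.3: "If an individual cannot safely be given DP, that individual will not be given medication for presumptive treatment".
- Table 4 and section 17.3: people not eligible for DP get an RDT, and go to a health facility if it is positive.
- Appendix K: every regimen that field staff can record at the intervention visit is DP.
- Appendix Z: the committee oversees the study drug, described as DP or "artemether-lumefantrine (AL) as an alternative to DP", and later refers to use of either drug in TPE. It gives no condition for using AL.

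**The concern.** The protocol states two limits on AL in 1.6 and then, in 12.1, gives an instruction that ignores both. Someone following 12.1 alone would direct a woman in early pregnancy with a positive RDT to a drug that 1.6 calls contraindicated for her. Someone following 7.3 would refer the same woman, if she lives in a TPE locality, for a drug that is safe for her. The text does not say which section governs.

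The second mismatch concerns oversight. Section 8.5 ties expedited reporting to the study drugs, and section 16.3 ties the stopping guidelines to serious adverse events attributed to them. Section 16.1 cites Appendix Z for full details of the committee. If the committee's terms treat AL as an alternative study drug and the protocol's intervention section does not, the committee and the investigators could differ on which exposures and events come under those rules.

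**Working it through.** There is no plan figure to reproduce. The check sets the sections side by side, with one rough calculation of scale.

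**Step 1. Do people limited by 1.6 reach the instruction in 12.1?**

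- TPE arm, intervention visit: 7.3 excludes all pregnant women from DP, which includes the first trimester. It excludes infants under 7 kg, which includes those under 5 kg. People excluded from DP are tested by RDT. So both groups in 1.6 are tested, and a positive result falls under 12.1 as well as 7.3.
- RACD arm, intervention visit: Table 3 sets no exclusion for pregnancy or weight, so both groups are tested. A positive result falls under 12.1, 4.1 and 7.2. Sections 12.1 and 4.1 name only AL; 7.2 also names oral quinine.
- End-line survey, both arms: Table 3 lists no exclusions, and Table 4 has RDT testing with referral but names no drug. The same Table 4 wording applies at the 6-9 month visit. In the text available, 12.1 is the only wording I find that names a drug for these visits.

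The overlap is therefore real, and it is not confined to TPE residents who cannot take DP.

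**Step 2. Is 7.3 consistent with itself?** Yes. Giving no presumptive drug and referring positives for a safe drug answer different questions. The conflict on treating positives lies between 12.1 and 4.1 on one side and 1.6, 7.2 and 7.3 on the other.

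**Step 3. Does Appendix Z match the intervention text?** No. Sections 7.3 and 17.3, Table 4 and the Appendix K regimen table all describe presumptive treatment with DP or none. Appendix Z alone presents AL as standing in for DP.

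**Step 4. Scale.** Section 1.3 reports 42 RDT-positives among 8,355 people screened: 42 / 8,355 = 0.50%. Section 14.1 expects about 6,000 intervention encounters and 5,600 people in the end-line infection survey. If everyone in each were tested and the past yield held:

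- Intervention visits: 6,000 × 42 / 8,355 = about 30 positives.
- End-line survey: 5,600 × 42 / 8,355 = about 28 positives.

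The first figure is generous, because most TPE residents receive DP without a test. Only those positives who are in the first trimester or under 5 kg meet the contradiction with 1.6. The documents do not give that share.

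**The case against.** The strongest reply is that the operative text is safe in practice. Section 12.1 is a laboratory section. It sends positives to a health facility for work-up, so the choice of drug is in clinical hands. For TPE residents who cannot take DP, the more specific rule in 7.3 requires a drug that is safe for them. This stands as a limit on the risk. It does not remove the contradiction: 12.1 names AL as the only treatment, does not defer to 7.3, and also covers visits and an arm that 7.3 does not.

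On Appendix Z, the reply is that it is a committee's terms of reference, marked for approval in December 2014, with no treatment instruction. AL does need oversight, since RACD positives receive it and the SAE outcome in Table 6 counts events related to DP or AL. That also stands, but it does not explain why AL is described as an alternative to DP.

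A reader might go further in four ways that the documents do not support:

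- **That Appendix Z allows presumptive AL for everyone who cannot take DP.** It never mentions those residents and gives no condition; it could mean a general substitute. Field staff following 7.3 and Appendix K have no route to presumptive AL.
- **That positives are concentrated in the groups named in 1.6.** The DP exclusions are much wider (fever, breastfeeding, cardiac, renal or hepatic problems, other drugs), and no breakdown of positives is given.
- **That people excluded from DP for QTc reasons are also barred from AL.** Table 3 lists lumefantrine among QTc-prolonging products, but only as recent treatment that rules out DP. The stated limits on AL are the two in 1.6.
- **That AL given in the study would go unrecorded.** The Appendix K regimen table has no AL entry, but the end-line questionnaire asks which study medication was taken and lists AL.

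**Conclusion.** The point holds as an inconsistency in the text. It is not a criticism of a design choice.

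The main part is that 12.1 and 4.1 cannot be read together with 1.6, 7.2 and 7.3 as one rule for treating RDT-positives. It concerns a safety limit that the protocol itself states, so it should be corrected even though few people are likely to meet it. The scale rests on the past yield of about 0.5% carrying over. The number in the two groups in 1.6 cannot be derived from the documents. The word contraindication applies only to the first trimester; below 5 kg the protocol's term is not indicated.

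The lesser part is that Appendix Z and the protocol disagree on what the study drug is. What follows from this is uncertainty in the committee's remit, and no more. No effect on power or on the primary analysis follows from either part.

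**What to change.** 1. Reconcile 12.1 and 4.1 with 7.2, 7.3 and 1.6, so that one statement governs treatment of RDT-positive participants in both arms and at every visit where an RDT is done. The other sections should refer to it.
2. Reconcile the study-drug wording in Appendix Z with 7.3, and check that the term study drugs in 8.5 and 16.3 has the same meaning. If AL has a role as an alternative to DP, 7.3, Table 3, Appendix K and the coverage definition in Table 6 need to say so. If it has none, the Appendix Z phrase needs to change.

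The clinical team and sponsor decide the content; no view is offered here on which drug rule is right. The cost is wording in the protocol and the committee's terms of reference, with the usual ethics notification. Sample size and analysis are unaffected.

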12.2 Filter paper sample collection

Blood spots will be collected onto filter paper for future molecular studies for research purposes only. Filter paper (Whatman 3MM) will be pre-cut into individual squares and stapled to a thick card that will serve as its cover. Blood spots will be collected onto the filter paper in volumes of approximately 25µl aliquots per blood spot (4 blood spots per sample). Filter paper samples will be labelled with the individual's bar code or ID number on the covering cardboard, and will be allowed to dry at ambient temperature and relative humidity before closing the card over the filter paper (like closing a matchbook). Filter paper samples will be transported from the field in a zip lock bag and will be placed into a stock card filter paper box for final storage at -20°C.

12.3 Microtainer blood collection

Microtainers with dry EDTA anticoagulant will be used to collect 250µl of blood for research purposes only. This blood will be collected from secondary cases identified at the RACD intervention visit during case investigation. Microtainer blood samples will also be collected from index cases, secondary cases, and a sample of RDT-negative controls at the 6-9 month follow-up survey. Whole blood samples may be stored at 4°C for up to 24 hours before centrifugation to separate plasma from blood cells.

12.4 Antibody and DNA extraction

Antibodies and DNA will be extracted from dried blood spots using the Chelex method with saponin.

Whole blood samples (collected at the 6-9 month Follow-up visit and at the end-line survey visit near the end of the study, expected mid 2017) should be centrifuged within 24 hours to separate out the plasma. Pelleted blood cells will be resuspended with PBS buffer, and can be stored at 4°C for up to one week before DNA is extracted using a Qiagen blood extraction kit at the National Reference lab for the appropriate molecular tests.

Plasma and DBS antibodies will be stored in cryovials ideally at -20°C or lower. DNA will be stored in cryovials at -20°C.

12.5 LAMP

DNA samples will first undergo LAMP testing using the Pan-LAMP detection kit (which detects DNA sequences common to all *Plasmodium* species), followed by testing with the *Pf*-LAMP detection kit if Pan-LAMP positive. These studies will be performed only for research purposes and will have no impact on the clinical management of study participants.

12.6 PCR

All RDT or LAMP positive samples as well as 10% of negative samples will undergo nested cytochrome B PCR testing with species specific identification using a restrict digest,⁸⁻¹⁰[32] Other molecular studies may include analyses of polymorphisms in parasite and/or human genes for mutations that may impact on clinical malaria, and genotyping of malaria parasites. These studies will be performed only for research purposes and will have no impact on the clinical management of study participants.

12.7 Genotyping

Genotyping of *Pf* will consist of a panel of microsatellites and/or SNPs located throughout the genome. Briefly, DNA samples will be amplified in a multiplex pre-amplification step followed by amplification of microsatellites in individual reactions using fluorescently tagged primers, and sized using denaturing capillary electrophoresis. Multi-locus genotypes from mixed infections will be reconstructed, where possible, by quantifying alleles at each locus. Genotyping of additional loci will be performed as needed. These studies will be performed only for research purposes and will have no impact on the clinical management of study participants.

12.8 QT-NASBA for gametocytes

RNA will be extracted from DBS using the Boom extraction method.[33] Sub-microscopic gametocyte density will be measured using the *Pf* 25S mRNA real time QT-NASBA.[34] These studies will be performed only for research purposes and will have no impact on the clinical management of study participants.

12.9 ELISA

Serology, a test of past infection as assessed by the presence of antimalarial antibodies, may improve the identification of hot spots. ELISA assays will be performed using previously described methods[6]. Briefly, plasma or DBS antibodies will be assayed to detect antibodies against the *Pf* blood stage antigens merozoite surface protein-1 (MSP-1₄₂) and apical membrane antigen-1 (AMA-1), both biomarkers of *P. falciparum* exposure.[35] Other antigens that are sensitive and specific for recent exposure (currently undergoing evaluation) may also be used. ELISA assays will be performed in duplicate and optical densities recorded with an ELISA reader. Other serologic platforms (bead array, protein microarray) may also be used

analyze responses to multiple antigens if available. These studies will be performed only for research purposes and will have no impact on the clinical management of study participants.

12.10 Sample storage for future studies (for research purposes only)

After the study period, samples will be stored for future research. The consent forms for this study include a statement about future testing for research purposes only. Samples will be stored for 25 years, reason being that if there are new malaria cases after elimination, it will be helpful to have past samples for molecular testing. The WHO recommends an isolate bank because comparing new strains to past strains will help distinguish between imported and local infection[36]. Re-emergence of new cases could occur more than 20 years after elimination. For example, North and South Korea eliminated malaria in the 1970s, but then experienced a re-emergence of the disease in the 1990s.

13 Data management

13.1 Quality assurance & quality control

All members of the study personnel will be trained in the project objectives, methods of effective communication with study participants, collection of high quality data and principles of ethical research practice. Study personnel members will receive additional training specific to the tasks they will perform within the project including interviewing techniques, administration of surveys, completing questionnaires, and use of tablet devices. Standard Operating Procedures (SOPs) will be written for all project activities and booklets of all relevant documents provided to each member of the project team. Study group meetings will be conducted by the principal investigator to assess progress of the study, address any difficulties, and provide performance feedback to the members of the study group. Any corrections to data collection forms will be made by striking through the incorrect entry with a single line and entering the correct information adjacent to it, according to Good Clinical Practice guidelines.[37] The correction will be initialed and dated by the investigator.

13.2 Records & storage

The principal investigator will maintain appropriate medical and research records for this study in compliance with the principles of good clinical practice and regulatory and institutional requirements and in compliance of the requirements for the protection of confidentiality of participants. Only study personnel members will have access to these records. All forms with participant names will be kept in a locked cabinet, when not in use, and the key kept by the local investigators. Participants will be identified by their study ID number, and participant names will not be entered into the computerized database. Data will be stored for at least 5 years. Authorized representatives of the sponsor, the ethics committee(s) or regulatory bodies may inspect all documents and records required to be maintained by the investigator. The investigators will allow all requested monitoring visits, audits or reviews.

14 Statistical issues

14.1 Study population

Overall:

Based on the most recent census data, the overall population in the 77 study localities is estimated at 211,189 individuals. However we expect that some localities will have no incident cases and therefore not receive any intervention. In the previous two transmission seasons, only 63 of the 77 localities had at least one case. Our sample size calculations are further based on the expected at-risk population within the 63 localities, or EA that had at least one case in the previous three seasons, a total of 55,928 individuals. The size of the expected at-risk within localities varies greatly, therefore we used the harmonic mean of

population size in localities with at least one case (656 per locality) to represent the effective sample size of the study in calculations of the design effect.

Target Area:

As defined above in section 4.4, the Target Area for TPE localities is defined as all individuals residing within 200m of an index case that is detected in passive surveillance and resides in a TPE study locality, with individuals residing immediately beyond 200m included if a minimum of 30 enrolled individuals is not reached within 200m. The Target Area for RACD localities is defined as all individuals residing within 500m of an index case that is detected in passive surveillance and resides in a RACD study locality. Sample size calculations for the secondary outcome measures of seroprevalence and infection prevalence are based on the population of the Target Areas.

The sample size for the Target Area assessments is estimated from incidence in the previous transmission season, and the expected drop in incidence among those in the TPE arm; resulting in an estimated 200 index cases total with 30 individuals screened or treated in the Target Areas around each case. With 200 index cases, we expect about 6000 encounters where individuals will receive a study intervention (either TPE or RACD). Based on preliminary RACD data, we anticipate 10% of these encounters will occur in individuals who previously received an intervention during the study period (repeated or overlapping Target Areas). For the follow-up end-line seroprevalence survey, these individuals will only be sampled once. Thus the effective sample size for the seroprevalence outcome measured in the Target Area population is expected to be 5400. Of note, the first index case for each Target Area will not be included since this person's malaria exposure occurred pre-intervention.

For the follow-up end-line infection prevalence survey, index cases will also be included as they will also be at risk for subsequent infection. Thus the effective sample size for the infection prevalence outcome measured in the Target Area population will be 5400 individuals screened plus 200 index cases, or 5600 individuals.

Adherence evaluation:

Adherence will be measured on a subsample that includes only the individuals in the Target Areas surrounding the first index case in each locality. We expect that 22 localities in the TPE arm will have at least one index case, and at least 30 individuals will be assessed for DP treatment per Target Area, for a total sample of 660 individuals.

